Description of Study Design:	
The study will be an open-label, crossover study (n=12 healthy subjects) over ~10 weeks includes four study sessions with up to a 45 day screening period with one week washout period between study sessions.
 
The study contains four study sessions:
 
• Study Session 1: Exelon[®] TDS containing 9 mg (4.6 mg/24 h) of rivastigmine base to be worn for ~9 h.• Study Session 2: Rivastigmine generic TDS containing 6.9 mg (4.6 mg/24 h) of rivastigmine base to be worn for ~9 h.• Study Session 3: Exelon[®] TDS containing 9 mg (4.6 mg/24 h) of rivastigmine base to be worn for ~9 h. The heating pad will be set to induce a skin temperature of 42.0 ± 4°C and applied for 1 hour 30 minutes at 5 h after application of the TDS.

Study Session 4: Rivastigmine generic TDS containing 6.9 mg (4.6 mg/24 h) of rivastigmine base to be worn for ~9 h. The heating pad will be set to induce a skin temperature of $42.0 \pm 4^\circ\text{C}$ and applied for 1 hour 30 minutes at 5 h after application of the TDS.

A) Pharmacokinetics (PK)

Each subject will be his/her own control (pre-dose blood sample) and each subject will sign an institutional review board–approved consent form explaining the purpose, nature, risks, benefits, and duration of the study. The study will be conducted in accordance with good clinical practice guidelines and with the ethical principles originating in the Declaration of Helsinki.

The subject's skin in the area of application (upper arm) will be relatively free of hair before TDS application. Blood samples (approximately 4 mL each) will be drawn in BD vacutainer tubes. Blood samples will be obtained as follows:

- Within 60 min pre-application and then up to ~12 h after TDS application.

B) Residual Drug Analysis of Rivastigmine TDS

In conjunction with the above described study, residual drug analysis will also be conducted for the previously worn Exelon® and rivastigmine generic TDS from Study Session 1-4.

- Prior to administration to the subject as described in Part A, TDS will be weighed and the weight recorded.
- The pouch, release liner and all items coming into contact with the TDS (gloves, forceps, etc..) applied in Part A will be retained for analysis.
- The used TDS will be retained for drug content analysis.
- All items coming into contact with the TDS during removal from the subject will be stored in a separate labeled sealable pouch until analyzed for drug content.

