5 PHARMACOKINETICS AND STATISTICAL CONSIDERATIONS

5.1 Analyses

Rivastigmine concentrations will be measured in serum samples collected from each subject. Blood samples (approximately 4 mL or 5 mL (~1 tsp)) will be collected within 60 min of pre-application and then at 2 h, 3 h, 4 h, 5 h, 5 h 15 min, 5 h 30 min, 5 h 45 min, 6 h, 6 h 15 min, 6 h 30 min, 7 h, 7 h 30 min, 8 h, 8 h 30 min, 9 h, 9 h 15 min, 9 h 30 min, 10 h, 11 h and 12 h post-TDS application.

Non compartmental analyses (NCA) will be conducted to estimate the PK parameters such as: maximum serum concentration (C_{max}), apparent elimination rate constant (k); apparent half-life ($t_{1/2}$), calculated as $0.693/k$; AUC_{0-last} of the serum concentration–time determined by the linear trapezoidal method (TDS); and AUC value extrapolated to infinity (AUC_{inf}), calculated as the sum of AUC_{0-last} and the area extrapolated to infinity: $AUC_{inf} = AUC_{0-last} + C_{last}/k$ where C_{last} would be the last quantifiable concentration. All NCA analyses will be conducted using Phoenix[®] WinNonlin[®] 6.4 (Pharsight, a Certara Company, CA).

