5.3 Final Analysis Plan

An objective of this study is to investigate the influence of heat application on the PK parameters of rivastigmine after using a RLD or generic TDS. The primary PK parameters

to be compared are 1) C_{max} , before and after heat application; 2) AUC before and after heat application consistent with similar PK studies^(6,7). Determine PK parameters (C_{max} , AUC) of rivastigmine in healthy adults after using Exelon® and rivastigmine generic TDS for the purpose of IVIVC by collecting data. Complimentary in vitro data will be collected using human skin.

IVIVC will be conducted comparing PK parameters and profiles to predicted PK parameters and profiles using IVPT results. Multiple methods will be implemented to develop an IVIVC. The first method is to compare the steady state concentrations. The predicted steady state concentration using our current IVPT data will employ the following formula:

$$C_{ss} = \frac{J_{ss} * A}{CL}$$

C_{ss} =steady state serum concentration; J_{ss} =steady state flux; A=area; CL=clearance

The second method will compare the PK profiles of the clinical and IVPT study by predicting rivastigmine concentrations at each time point in the IVPT study and comparing it to the PK profile. The third method will be to determine and compare residual TDS analysis between in vitro and in vivo.

Intra-procedure comparisons:

For Study Session 1-4:

- C_{max} will be compared among the following time periods: 0-5 h, 5 h-6 h 30 min, 6 h 30 min-9 h and 9-12 h post TDS application
- AUC: will be compared among the following time periods: 0-5 h, 5 h-6 h 30 min, 6 h 30 min-9 h and 9-12 h post TDS application

Inter-procedure comparisons:

For Study Session 1-4: Both C_{max} and AUC will be compared among procedure groups for the following time periods: 5 h -6 h 30 min.

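### The between-session comparison of the 5 h to 6 h 30 min window makes no use of each session's pre-heat level, which costs precision and leaves any systematic session shift uncorrected

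*Combined protocol and SAP*

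**What the plan says.** The between-session rule in section 5.3 (Final Analysis Plan, inter-procedure comparisons) is: "Both C_{max} and AUC will be compared among procedure groups for the following time periods: 5 h -6 h 30 min". No model, scale, contrast or baseline term accompanies it.

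The pre-heat period is used elsewhere in the same section. The primary parameters include "AUC before and after heat application consistent with similar PK studies", with Cmax treated likewise. The intra-procedure list states, for all four sessions, "C_{max} will be compared among the following time periods: 0-5 h, 5 h-6 h 30 min" and "AUC: will be compared among the following time periods: 0-5 h, 5 h-6 h 30 min", followed by two later windows.

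The Protocol Summary (Description of Study Design) says that in Sessions 3 and 4 the heating pad is "applied for 1 hour 30 minutes at 5 h after application of the TDS". Section 5.1 schedules a pre-application sample and "then at 2 h, 3 h, 4 h, 5 h, 5 h 15 min, 5 h 30 min", and so on to 12 h. The design is summarised as "The study will be an open-label, crossover study (n=12 healthy subjects) over ~10 weeks". The own-control statement in the Summary refers to the sample before patch application, not to the level just before heat.

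**The concern.** Sessions 1 and 3 are both unheated reference product until 5 h, and Sessions 2 and 4 are both unheated generic. A difference between paired sessions before 5 h therefore cannot be a heat effect. It reflects how much that patch delivered on that day, or a period effect. A patch that is delivering more at 5 h will probably still be doing so at 6 h, so part of the noise in the heated window can be predicted from samples already drawn. The between-session rule leaves that information out.

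Two things are at stake.
- **Heat effect within a product:** precision in a 12-subject trial, and protection if sessions differ systematically.
- **Heat effect between products:** section 2.2 asks whether heat affects the two products differently. Comparing Session 4 directly with Session 3 answers a different question, because any difference in level that existed without heat is included.

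**Working it through.** **1. The plan's own figure.** Section 5.2 gives mean 166, SD 50, tolerated error 25%, type 1 error 5% and type 2 error 20%. Its formula gives n = (1.960 + 0.842)² × (50/166)² / 0.25² = 11.39, rounded up to 12. Power at 12 is Φ(√12 × 0.25 / (50/166) − 1.960) = 0.820. The stated 82% reproduces with two-sided alpha. This calculation concerns the error of one session's 24 h AUC. It contains no within-subject variance and does not size the between-session contrast.

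**2. Assumptions.** The documents give neither of these, so both are illustrative:
- s, the within-subject session-to-session SD on the log scale: 0.25, range 0.15 to 0.35.
- r, the correlation within a session between the pre-heat and heated-window deviations: 0.3, 0.5 and 0.8.

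n = 12 is from the Protocol Summary.

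**3. Precision of one heated/unheated ratio** (Session 3/1 or 4/2). The 95% CI factor is exp(t × SE).
- Unadjusted: SE = √2 × s / √12 = 0.102; t(11) = 2.201; factor 1.25 (1.14 at s = 0.15, 1.37 at s = 0.35).
- Covariate: multiply SE by √(1 − r²). Estimating a slope from 12 pairs also costs one degree of freedom (t(10) = 2.228) and inflates the variance by about 1 + 1/(12 − 3) = 1.11.
- Ratio to pre-heat: multiply SE by √(2(1 − r)); t(11).

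| r | Unadjusted | Covariate | Equivalent n, 12/[(1 − r²) × 1.11] | Ratio to pre-heat |
|---|---|---|---|---|
| 0.3 | 1.25 | 1.26 | about 12 | 1.30 |
| 0.5 | 1.25 | 1.23 | about 14 | 1.25 |
| 0.8 | 1.25 | 1.15 | about 30 | 1.15 |

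The covariate gains little at r = 0.5, clearly helps at 0.8, and gains nothing at 0.3. The ratio gains nothing at r = 0.5 and loses below it.

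**4. Bias.** Suppose heat has no effect. Simulation of 20,000 trials (s = 0.20, r = 0.7, paired t-test on logs) gave:

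| Systematic shift, heated session | Unadjusted ratio | False positives, unadjusted | False positives, ratio to pre-heat |
|---|---|---|---|
| none | 1.00 | 5% | 5% |
| 10% | 1.10 | 19% | 5% |
| 20% | 1.20 | 53% | 5% |
| 25% | 1.25 | 70% | 5% |

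At s = 0.30 and r = 0.7 the unadjusted rates for the three shifts are 11%, 27% and 38%. The first row matters most: purely random session differences leave the error rate at 5%.

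**5. What each adjustment removes.** With equal variances the covariate slope is about r, so a 10% systematic shift leaves 1.1^(1 − r): 4.9% at r = 0.5 and 1.9% at r = 0.8. The ratio removes it all. The two adjustments are therefore not interchangeable.

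**6. Product comparison.** Let generic/reference without heat be g, and let both products have the same heat ratio h. Then S4/S3 = g × h / h = g, which differs from 1 although heat acts equally on both. The double ratio (S4/S2)/(S3/S1) = h/h = 1, with no pre-heat adjustment needed. It uses four sessions, so its unadjusted SE is 2 × 0.25 / √12 = 0.144 and its factor exp(2.201 × 0.144) = 1.37. Precision is scarcer for this contrast.

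**The case against.** A reader might infer that the plan ignores the pre-heat level and will therefore report ordinary session-to-session variation as a heat effect. The documents do not support that.

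- The intra-procedure comparisons set 0-5 h against the heated window in every session, including the unheated ones. Pre-heat Cmax and AUC will be computed, so a shift between paired sessions could be seen in planned output. This stands. However, the contrast is not carried into the between-session comparison, and its AUC version sets a 5 h window against a 1.5 h window with no stated division by length.
- Random variation in site, adhesion or day averages out in a paired comparison. This stands: the cost is precision, and bias needs a systematic shift. The text I could read states no session order and so does not exclude a period effect. Part of the document was not available to me and may state the order, so the bias is a possibility and not a finding.
- A constant proportional product difference cancels in (S4/S2)/(S3/S1), and section 5.3 does not say that heated sessions will be compared directly. This stands too. The gap is that no contrast is named.
- Absolute levels under heat are a legitimate target, since section 2.1 links the safety concern to raised serum concentrations. Unadjusted values should therefore stay in the report.

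That the comparison is unadjusted is itself inferred from the plan's silence, but it is the plain reading of the sentence.

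**Conclusion.** The point holds in limited form. As written, the between-session comparison leaves out a pre-heat level that every session supplies, and it does not name the contrast that isolates a product difference in heat effect.

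The established consequence is lost precision if r is high enough. With n = 12 and s = 0.25 assumed, the CI factor is 1.25 against about 1.23 (r = 0.5) or 1.15 (r = 0.8). At low r nothing is gained. Bias is conditional: a systematic session shift would pass one-for-one into the unadjusted ratio, but nothing I could read shows that such a shift exists. Direct S4/S3 comparison would mix levels with heat effect, but the plan leaves open whether that will be done. The amendment is worthwhile and cheap; the gap does not by itself invalidate the comparison.

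**What to change.** In section 5.3, replace the inter-procedure sentence with the following.

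- **Model:** log Cmax and log AUC for 5-6.5 h, with terms for subject, period, product, heat and product-by-heat, and log AUC over 2-5 h from the same session (divided by 3 h if shown as an average level) as covariate. Prefer this to the 5 h concentration alone, which carries assay error and is also the first point of the outcome window. In the 2-5 h trapezoidal AUC that sample has weight 0.5/3, one sixth. The period term can be estimated only if session order varies between subjects. If all subjects follow the numbered order, period cannot be separated from treatment, and the last two items below become more important.
- **Product comparison:** the product-by-heat term, that is (S4/S2)/(S3/S1).
- **Unadjusted values:** reported alongside.
- **Sensitivity analysis:** the ratio to pre-heat, heated over unheated. It fully removes a systematic proportional shift but loses precision when r is below 0.5.
- **Negative control:** the AUC 2-5 h ratios S3/S1 and S4/S2 with confidence intervals. They should be near 1, and a clear departure signals a session effect.

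The cost is analysis wording and one extra model term, with little gain if r is low. No new subjects, samples or procedures are needed.
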